4.7. Pharmacokinetic Evaluations

Pharmacokinetic analyses are not applicable to this study.

4.8. Safety Analyses

Safety analyses will be conducted using the SAF.

4.8.1. Adverse Events

Adverse events will be coded using MedDRA and displayed in tables and listings using System Organ Class (SOC) and Preferred Term (PT) separately for ocular and non-ocular events.

Analyses of AEs will be performed separately for those events that are considered pre-treatment and treatment emergent, where treatment emergent is defined as any adverse event with onset after the administration of study medication through the end of the study or any event that was present at baseline but worsened in intensity.

AEs are summarized by subject incidence rates, therefore, in any tabulation, a subject contributes only once to the count for a given adverse event (SOC or PT).

AEs will be tabulated by treatment group with respect to their severity (mild, moderate, severe) and relationship (unrelated, unlikely, possible, probable, definite) to the IP. The number and percentage of subjects with any treatment-emergent adverse event will be tabulated by treatment group and overall with respect to their severity and relationship to the IP. In these tabulations, each subject will contribute only once (i.e., the most related occurrence or the most intense occurrence) to each of the incidence rates in the descriptive analysis, regardless of the number of episodes.

No formal hypothesis-testing analysis of adverse events incidence rates will be performed.

All missing dates of events that occur will be queried for a date. If no date is obtained, the following imputation rules will apply:

- For start dates, missing months and days will be imputed as '01', provided this occurs on or after the date of first study drug administration. Otherwise, the day or month (as appropriate) of the first administration of study drug will be used.
- For stop dates, missing months will be imputed as '12' and missing days will be imputed as the last day of the month. If this creates a date after discontinuation/completion, the date of discontinuation/completion will be used.

Sponsor:	AxeroVision, Inc.		
Protocol:	AXR201901		
Document Version No.:	1.1	Document Date:	26-OCT-2020

Where an AE is associated with a partially or fully missing start date or time, and it is unclear as to whether the AE is treatment emergent, it will be assumed that it is treatment emergent.

The imputed dates will only be used to classify events as pre-treatment or treatment emergent. Imputed dates will only be used in the table analyses. Listings will display the available date data.

All AEs occurring on study will be listed in separate subject data listings for ocular or non-ocular events with a flag for those that are treatment emergent.

By-subject listings also will be provided for the following: subject deaths; serious adverse events; and adverse events leading to withdrawal.

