- Determine if the subject is eligible to continue in the study. Do not continue screening any subject who does not meet eligibility requirements. Any subject who does not meet eligibility requirements will be designated as a Screen Failure.
- Instruct the subject to discontinue using all prohibited medications for the remainder of the study.
- If the subject is qualified, a four-week supply of commercial lid wipes will be provided.
- Schedule the subject to return for Visit 2 (Day 1) and remind subjects to bring the remaining lid wipes to Visit 2.

* May be performed at any time during the visit in order to facilitate subject and site schedules.

5.1.2. Visit 2 (Randomization): Day 1

Visit 2 will occur 14 (± 2 days) after Visit 1 (Screening). The following will be performed/assessed in both eyes:

- Evaluate continued eligibility
- Subject-rated symptom assessments (in this order):
 - Individual symptom assessment via VAS
 - OSDI
 - Modified BLISS
- Use of any concomitant medications since the last visit

- Occurrence of any AEs since the last visit
- BCVA
- Slit-lamp biomicroscopy and external eye exam
- TBUT
- FCS
- Investigator-rated assessment of signs of MGD
 - See Appendix 3. Assessment of Efficacy for full description of Investigator-rated assessments for objective signs of change from baseline
- LGS (at a subset of sites)
- Wait 15-20 minutes after LGS before proceeding
- Unanesthetized Schirmer test
- IOP
- Safety laboratory blood draw
- Determine if subject is eligible for randomization

For eligible subjects, the following is the process regarding administration of Double-Masked IP whereby the trained site staff will conduct the following procedures:

- Enter subject information into IWRS to determine randomization code and Kit Number. Cohort 1 versus Cohort 2 will be part of the Interactive Web Response System (IWRS) input
- Show the subjects an instructional video on applying the investigational product. Review Subject Dosing Instructions document, reiterating that the subject should administer IP across the entire surface (corresponding to the tarsal plate) of the upper and lower eyelids of both eyes
- Subject will self-administer first dose of double-masked IP in clinic under the supervision of site staff. The site staff will record the Day 1 dosing time in the source document.
- Assess for occurrence of any IP related AEs

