- Event occurring before dosing.
- Event or intercurrent illness due wholly to factors other than IP use.

Unlikely:

- Poor temporal relationship with IP use.
- Event easily explained by subject's clinical state or other factors.

Possible:

- Reasonable temporal relationship with IP use.
- Event could be explained by subject's clinical state or other factors.

Probable:

- Reasonable temporal relationship with IP use.

- Likely to be known reaction to agent or chemical group, or predicted by known pharmacology.
- Event cannot easily be explained by subject's clinical state or other factors.

Definite:

- Distinct temporal relationship with IP use.
- Known reaction to agent or chemical group, or predicted by known pharmacology.
- Event cannot be explained by subject's clinical state or other factors.

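### The SAP's start-date imputation for adverse events ignores the recorded stop date, so an event that ended before first dose can be counted as treatment-emergent

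*SAP*

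**What the plan says.** All of the rules are in SAP 4.8.1 (Adverse Events).

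- **When imputation applies:** "All missing dates of events that occur will be queried for a date. If no date is obtained, the following imputation rules will apply".
- **Start date, first step:** "For start dates, missing months and days will be imputed as '01', provided this occurs on or after the date of first study drug administration".
- **Start date, fallback:** "Otherwise, the day or month (as appropriate) of the first administration of study drug will be used".
- **Stop date:** a missing month becomes 12 and a missing day becomes the last of the month, capped at discontinuation or completion. Nothing links this to the start-date rule.
- **Use of imputed dates:** "The imputed dates will only be used to classify events as pre-treatment or treatment emergent".
- **Definition:** "treatment emergent is defined as any adverse event with onset after the administration of study medication through the end of the study", or present at baseline and later worse in intensity.
- **Default:** where the start date or time is wholly or partly missing "and it is unclear as to whether the AE is treatment emergent, it will be assumed that it is treatment emergent".

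Pre-dose events do enter the database. Protocol 5.1.2 lists the query "Occurrence of any AEs since the last visit" at Visit 2 ahead of the in-clinic dose, and a separate check for product-related events follows dosing. Protocol 8.3 has the date and time of both onset and resolution recorded on the eCRF.

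**The concern.** The fallback looks only at the partial start date and the first-dose date. It does not ask whether the event had already resolved, so it can produce an onset later than the event's own recorded resolution. No reading of the plan intends that, and the imputed date then feeds the classification.

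Safety and tolerability are the primary objective. SAP 7.1 plans separate pre-treatment and treatment-emergent tables and marks the two treatment-emergent overviews as topline. A misplaced event is added to one set and lost from the other. Pre-dose ocular complaints are plausible here, because subjects suspend tear substitutes and their usual lid hygiene from Visit 1. Two programmers working from the present text could also classify the same record differently.

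**Working it through.** The plan gives no figure on this point, so there is none to reproduce. The check applies the stated rule to test dates and then sizes the exposure.

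**1. The rule applied literally.** Assumed first dose: 20 August 2020 (for illustration; the documents give no dosing dates). Let c be the start date with '01' in each missing field. If c is on or after first dose, the imputed start is c. Otherwise each missing field takes the first-dose value.

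| Recorded start | Recorded stop | c | Imputed start | Result |
|---|---|---|---|---|
| Aug 2020, day unknown | 14 Aug | 1 Aug | 20 Aug | 20 − 14 = 6 days after the stop |
| 2020, day and month unknown | 14 Aug | 1 Jan | 20 Aug | 6 days after the stop |
| Aug 2020, day unknown | 25 Aug | 1 Aug | 20 Aug | before the stop; true status unknown |
| Jul 2020, day unknown | 14 Aug | 1 Jul | 20 Jul | before first dose; pre-treatment |
| Sep 2020, day unknown | 9 Sep | 1 Sep | 1 Sep | after first dose; treatment-emergent |

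The first two rows show the fault: the event was over before dosing, yet its imputed onset is the first-dose date. The third row is the case that the default is meant for.

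**2. Does the imputed date settle the class?** Not by itself. The definition requires onset after administration, and the fallback gives a date equal to first dose with no time. If 'after' is read strictly on dates, the date alone would make every fallback event pre-treatment, including those that truly followed dosing. If an onset on the first-dose date counts, rows 1 and 2 become treatment-emergent. The default could decide the matter, but the SAP does not define 'unclear' and does not rank that sentence against the imputed date.

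**3. Which pre-dose days are exposed.** Protocol 5.1.2 puts Visit 2 at 14 days after Visit 1, give or take 2, so the gap g is 12 to 16 days. The day-unknown fallback reaches first dose only for starts in the same calendar month. In a month of L days with L > g, the average share of the g pre-dose days in that month is 1 − (g + 1)/(2L). Over the 366 possible first-dose dates of 2020, assumed equally likely, this becomes 1 − 12(g + 1)/(2 × 366):

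- g = 12: 1 − 78/366 = 0.787
- g = 14: 1 − 90/366 = 0.754
- g = 16: 1 − 102/366 = 0.721

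This is a share of calendar days on which a start could fall, under an assumed uniform spread. It is not a share of adverse events.

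**4. Effect of one record.** SAP 2.1 plans about 42 subjects per active arm and 42 on vehicle, and SAP 4.2.3 pools vehicle. One reclassified subject moves an incidence by at most 1/42 = 2.4 percentage points. It is 'at most' because a subject counts once per tabulation, so someone already counted there adds nothing.

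**5. With a stop-date check.** Rows 1 and 2 become pre-treatment. Row 3 stays treatment-emergent by the default. Rows 4 and 5 do not change.

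**The case against.** The strongest reply is that the SAP already allows the right answer. The default covers only cases whose status is unclear, and an event with a recorded stop before dosing is not unclear. The definition also requires onset after administration. Stop dates are imputed too, and classification is the only stated use of imputed dates, which suggests that stop dates were meant to count. This stands as a reasonable reading of intent. It does not close the gap, because no sentence says how a stop date enters the classification or that any of this overrides the imputed start.

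Four stronger readings are tempting, and the documents do not support them.

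- **That such events will be treatment-emergent.** The text supports only that they can be, for the reasons just given.
- **That about three in four pre-dose events with an unknown day would be misclassified.** The 72% to 79% counts calendar days under an assumption. It also covers starts of events that continued past dosing, which are not the fault described here.
- **That the comparison between arms is distorted.** The rule is identical in every arm, pre-dose events cannot depend on treatment, and SAP 4.8.1 plans no test of incidence rates. An equal added rate does not bias the absolute difference in expectation.
- **That the rule conflicts with the protocol's causality categories.** Protocol 8.2 puts "Event occurring before dosing" under the unrelated category, but the investigator assigns relationship and an imputed date does not change it. The listings also show the dates as recorded and flag treatment-emergent events, so a misplaced case can be seen.

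**Conclusion.** The point holds as a gap in the rule. SAP 4.8.1 can give an adverse event an onset later than its known resolution, and nothing in the section ensures that an event over before dosing is kept out of the treatment-emergent tables.

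The effect is likely small. It needs a missing start day or month that a query failed to resolve, together with a stop date before first dose. The number of such records cannot be known from the documents. Any error overcounts treatment-emergent events rather than hiding them, although it also removes the event from the pre-treatment tables. The ceiling of 2.4 points per affected subject assumes arms of 42. This is a worthwhile clarification of the primary safety output and does not threaten the trial's conclusions.

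**What to change.** In SAP 4.8.1, before the imputation rules, state that:

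1. an adverse event whose recorded stop date is before first dose is pre-treatment, and likewise one with a partial stop date if every date compatible with it is before first dose;
2. an imputed start date may not be later than the stop date;
3. this check comes before both the first-dose-date fallback and the default to treatment-emergent, which then apply only to cases still unresolved.

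Where the eCRF shows that the event was reported before dosing at Visit 2, classify it as pre-treatment unless it later worsened. This last part is conditional, because the fields listed in Protocol 8.3 do not include the reporting visit or query, and Visit 2 also has a post-dose check.

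The cost is a few lines of SAP text and a minor programming change. The stop-date check needs no new data, since resolution date and time are already collected.

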4.8.2. Laboratory Data

Clinical laboratory values will be expressed using conventional units.

The actual value and change from baseline to each on study evaluation will be summarized for each clinical laboratory parameter, including hematology and clinical chemistry. In the event of repeat values, the last non-missing value per study day/time will be used.

Shift from baseline tables to each on study evaluation will be provided by treatment group. The categories will include low, normal, high, and missing.

Values below the Lower Level of Quantification (LLQ) or above the Upper Level of Quantification (ULQ) will be imputed as one unit less or more respectively than the precision of measurement. <xxx will be computed to xxx-1, <xxx.x to xxx.x-0.1, etc. >xxx will be computed to xxx+1, >xxx.x to xxx.x+0.1, etc.

All laboratory data will be provided in data listings.

4.8.3. Dilated Ophthalmoscopy

Dilated ophthalmoscopy findings will be summarized descriptively, including the number and percent of subjects with normal and abnormal results for the retina and optic nerve results at Baseline and each study visit by treatment group and study or non-study eye. Summary statistics will be provided for the cup-to-disc ratio at each study visit by treatment group and study or non-study eye.

All dilated ophthalmoscopy findings will be provided in a data listing.

4.8.4. Intraocular Pressure

The actual value and change from baseline to each on study evaluation will be summarized for intraocular pressure (mmHg) for the study eye and non-study eye by treatment group. Counts and percentages of subjects by study eye and non-study eye with elevations in IOP at any point in the study will also be provided for the following elevation categories:

- IOP increase from baseline ≥ 10 mmHg

Sponsor:	AxeroVision, Inc.		
Protocol:	AXR201901		
Document Version No.:	1.1	Document Date:	26-OCT-2020

- Absolute IOP value >25 mmHg
- Absolute IOP value >30 mmHg

If a subject has an absolute IOP value >30 mmHg, they will be counted in both categories of ‘Absolute IOP value >25 mmHg as well as in ‘Absolute IOP value >30 mmHg’. All intraocular pressure data will be provided in data listing with elevation categories flagged.

4.8.5. **Best Corrected Visual Acuity**

The actual value and change from baseline to each on study evaluation will be summarized for the calculated logMAR score for the study eye and non-study eye by treatment group.

All BCVA data will be provided in data listings.

4.8.6. **Slit-lamp Biomicroscopy and External Eye Exam**

Slit-lamp biomicroscopy and external eye exam findings will be summarized descriptively, including the number and percent of subjects with normal/not present and abnormal/present results for lashes, eyelid edema, eyelid skin, conjunctival edema, palpebral conjunctival erythema, corneal infiltrates, corneal endothelial changes, and corneal edema results at baseline and each study visit by treatment group and study or non-study eye.

All slit-lamp biomicroscopy and external eye exam data will be provided in data listings.

4.8.7. **Urine Pregnancy Test and Concomitant Medications**

All urine pregnancy and concomitant medication data will be provided in data listings.

4.8.8. **IP Comfort Assessment**

The actual value and change from baseline to each on study evaluation will be summarized for the IP Comfort Assessment by treatment group.

All IP Comfort Assessment data will be provided in data listings.

Statistical Analysis Plan Template

Sponsor:	AxeroVision, Inc.		
Protocol:	AXR201901		
Document Version No.:	1.1	Document Date:	26-OCT-2020

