APPENDIX 5: SLIT LAMP BIOMICROSCOPY

The biomicroscopy exam should be performed with the slit-lamp using a beam width and intensity that provide optimal evaluation of the anterior segment.

This procedure will be performed in the same manner for all subjects observed at the Investigator's site. The site will record all ABNORMAL findings in the source document and the investigator will evaluate the ABNORMAL findings as Non-Clinically Significant (NCS) or Clinically Significant (CS). CS and NCS ABNORMAL findings will be recorded in the source documentation. However, only ABNORMAL CS descriptions will be captured in the eCRF.

Lashes

0 = Normal

1 = Abnormal

Eyelid

Edema

0 = Normal, no swelling of the lid tissue

1 = Abnormal

Skin

0 = Normal, including but not limited to thinning, pigment changes, dermatitis

1 = Abnormal

Conjunctiva

Edema

0 = Normal, no swelling of the conjunctiva

1 = Abnormal

Palpebral Conjunctival Erythema

0 = Normal, no redness of the conjunctiva

1 = Abnormal

Cornea

Infiltrates

0 = Absent

1 = Present

Endothelial Changes

0 = Normal, None

1 = Abnormal, pigment, keratoprecipitates, guttata

Edema

0 = Normal, None, transparent and clear

1 = Abnormal

Anterior Chamber

Cells

0 = Normal, No cells seen

1 = Abnormal (+ to +++ cells)

Flare

0 = Normal, No Tyndall effect

1 = Abnormal, Tyndall beam in the anterior chamber

Lens Pathology

0 = Normal, no opacity in the lens

1 = Abnormal, existing opacity in the lens; aphakic or pseudophakic eyes or other abnormal findings

Sclera

0 = Normal

1 = Abnormal

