14.4.2.5	Slit-lamp Biomicroscopy and External Eye Exam by Study/Non-study Eye – Safety Set
14.4.2.6	IP Comfort Assessment – Safety Set

* Topline table

Statistical Analysis Plan Template

Sponsor:	AxeroVision, Inc.		
Protocol:	AXR201901		
Document Version No.:	1.1	Document Date:	26-OCT-2020

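### The slit-lamp table counts abnormal eyes visit by visit but never eyes newly abnormal since Visit 2, so new and resolved lid or conjunctival findings can cancel out

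*SAP*

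**What the plan says.** Protocol 3.1.1 lists the slit-lamp and external eye examination among six safety endpoints, and safety and tolerability are the primary objective (Protocol 2.1). Protocol Appendix 5 codes 12 items, each 0 or 1, and the examination takes place at all five visits. Protocol 9.5 says only that the results will be summarised.

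SAP 4.8.6 gives the detail. It plans "the number and percent of subjects with normal/not present and abnormal/present results", by visit, by arm and by study or non-study eye, and it names eight of the items. SAP 7.1 has one matching table, 14.4.2.5, titled "Slit-lamp Biomicroscopy and External Eye Exam by Study/Non-study Eye"; the title mentions neither change nor shift. SAP 4.8.6 also states that "All slit-lamp biomicroscopy and external eye exam data will be provided in data listings".

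Other measures in the same plan are compared with the subject's own baseline:

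- Laboratory data (SAP 4.8.2): "Shift from baseline tables to each on study evaluation will be provided by treatment group".
- Modified BLISS: shift tables 14.2.11.3 and 14.2.11.4.
- IOP (SAP 4.8.4): change from baseline, plus counts of subjects "with elevations in IOP at any point in the study will also be provided".
- BCVA (SAP 4.8.5): change from baseline.

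**The concern.** A percentage abnormal at each visit describes the arm and not the eye. If one subject's lid edema clears while another's appears, the percentage stays the same. For a tolerability question the second event is the one of interest, and the table cannot show it.

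Both directions are plausible here. Subjects enter with moderate or worse lid-margin vascularity (Protocol 4.1, criterion 3), so some lid and conjunctival items may already be coded 1 at Visit 2. The product is described as anti-inflammatory (Protocol section 1), so some of those could resolve. A cream applied daily to the eyelid could also irritate the same tissues. An arm with more resolutions and more new findings than vehicle could then look the same as vehicle in table 14.4.2.5.

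**Working it through.** The plan states no figure on this point, so there is none to reproduce. The check has three parts.

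**1. Item count.** Appendix 5 codes lashes, eyelid edema, eyelid skin, conjunctival edema, palpebral conjunctival erythema, corneal infiltrates, endothelial changes, corneal edema, anterior chamber cells, anterior chamber flare, lens and sclera: 12 items. SAP 4.8.6 names the first 8. Then 12 − 8 = 4 are unnamed: cells, flare, lens and sclera.

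**2. What the visit counts determine.** Take one item in the study eye of one arm, with n eyes examined at both visits, b abnormal at Visit 2, x abnormal later, N new and R resolved.

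- x = b − R + N, so the table gives N − R = x − b (the net change) and nothing more.
- N lies between max(0, x − b) and min(x, n − b).
- The natural denominator for N is n − b, the eyes that could become newly abnormal.

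Inputs: n = 42, the approximate size of each active arm (SAP 2.1). The values of b and x are assumptions, because the documents give no baseline frequencies. With x = b, so that the table shows no change:

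| Abnormal at both visits | Eyes normal at Visit 2 | Possible new findings | Share of initially normal eyes |
|---|---|---|---|
| 2 of 42 | 42 − 2 = 40 | 0 to 2 | 0 to 2/40 = 5.0% |
| 6 of 42 | 42 − 6 = 36 | 0 to 6 | 0 to 6/36 = 16.7% |
| 12 of 42 | 42 − 12 = 30 | 0 to 12 | 0 to 12/30 = 40.0% |

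A case inside the bounds: with 8 of 42 abnormal at both visits, 5 resolved and 5 new, the table shows 19.0% twice. A count from Visit 2 would show 5/(42 − 8) = 5/34 = 14.7% new.

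**3. Where the problem arises.** The same identity shows when it does not.

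- If b = 0, then R = 0 and N = x: every abnormal eye is a new one. Exclusions 1, 4 and 6 (Protocol 4.2) bar iritis or uveitis, inflammatory eye conditions unrelated to MGD, and suspected infection. Cells, flare and corneal infiltrates should therefore be close to zero at Visit 2.
- If R = 0, then N = x − b exactly. Lens opacity, pseudophakia and guttata would not be expected to resolve by Day 22.
- What remains is mainly lid edema, lid skin, conjunctival edema and palpebral erythema. Lid-margin vascularity and bulbar hyperemia are graded 0 to 4 (Appendix 3) and analysed as change from baseline, so they are outside this point.

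**The case against.** The strongest reply is that the adverse event analysis already does this job. SAP 4.8.1 counts as treatment-emergent both events starting after dosing and events present at baseline that worsen, reports ocular events separately and counts each subject once. Tables 14.3.1.2.2, 14.3.1.4.2, 14.3.1.6.2 and 14.3.1.8.2 then give any-time subject counts by term, severity and relationship. For slit-lamp findings reported as events this stands. It does not cover the rest: neither Appendix 5 nor SAP 4.8.1 says that a new abnormal code must be recorded as an event.

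A second reply is that net change is visible and a masked vehicle arm supplies the contrast. That is also true, but the contrast is between values of N − R, so it does not separate irritation from improvement. Listings hold the subject-level data but give no count by arm.

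Some stronger readings are tempting and are not supported:

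- A reader might infer that safety findings would go undetected. The examinations are done, the data are listed, and events are reported.
- A reader might infer that the four unnamed items are left out. SAP 4.8.6 introduces its list as inclusive, and the title of table 14.4.2.5 is not limited to particular items.
- A reader might infer that slit-lamp is the only safety measure without a sound comparison with baseline. Dilated ophthalmoscopy (SAP 4.8.3) has the same by-visit form. The planned change from baseline for IP Comfort is no model either: the first rating comes about 2 minutes after the first dose (Protocol 5.1.2), while SAP 4.2.1 defines baseline as pre-dose.
- A reader might want a new field for worsening in eyes already coded 1. That would add an ungraded examiner judgement that overlaps adverse event reporting, and it is not needed here.

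**Conclusion.** The point holds, as a minor one. As planned, table 14.4.2.5 shows net change in slit-lamp findings but cannot show how many eyes became abnormal on treatment, except where a finding was also reported as an adverse event. The practical effect is confined mainly to the four lid and conjunctival items, which are also where local intolerance to the cream would be expected to show.

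The figures are logical limits on assumed counts and should not be read as expected rates. With 6 of 42 abnormal at both visits, the unseen number of new findings lies between 0 and 6 of 36 (0 to 16.7%). This assumes complete examinations at both visits in an arm of 42.

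The remedy also assumes that the 0/1 codes are in the database for every visit. Appendix 5 says that "only ABNORMAL CS descriptions will be captured in the eCRF", which limits the descriptions; the codes are needed for the table the SAP already plans.

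**What to change.** In SAP 4.8.6 and table 14.4.2.5, keep the by-visit counts and add, by treatment group and by study and non-study eye, the number and percent of subjects with a change from 0 at Visit 2 to 1 at any post-dose visit, for each item and for any item. The per-item denominator is Safety Set subjects whose eye was coded 0 on that item at Visit 2 and who have at least one post-dose examination. State the denominator for the any-item row as well; eyes with at least one item coded 0 at Visit 2 and a post-dose examination would be consistent.

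As a wording clarification, list all 12 Appendix 5 items in SAP 4.8.6.

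The cost is a few sentences in the SAP and a few extra rows in one table, from data already collected. Examinations, visits and the case report form do not change.

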1.2. Objectives of Statistical Analysis

The primary objective of this study is to evaluate the safety and tolerability of two concentrations (0.2% and 2.0%) of AXR-270 Cream in treating posterior blepharitis associated with MGD.

The secondary objective is to evaluate the efficacy of AXR-270 Cream in treating signs and symptoms of posterior blepharitis associated with MGD.

Sponsor:	AxeroVision, Inc.		
Protocol:	AXR201901		
Document Version No.:	1.1	Document Date:	26-OCT-2020

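### Slit-lamp and ophthalmoscopy tables give only by-visit prevalence per eye, so they cannot show how many subjects became newly abnormal, and no table counts subjects who lost BCVA

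*SAP*

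**What the plan says.** The primary objective (SAP 1.2) is to "evaluate the safety and tolerability of two concentrations (0.2% and 2.0%) of AXR-270 Cream". For the eye examinations, the SAP plans the following.

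- **Slit-lamp and external eye exam (4.8.6, Table 14.4.2.5):** the "number and percent of subjects with normal/not present and abnormal/present results for lashes, eyelid edema, eyelid skin" and five more items, ending with "corneal edema results at baseline and each study visit by treatment group and study or non-study eye".
- **Dilated ophthalmoscopy (4.8.3, Table 14.4.2.1):** "number and percent of subjects with normal and abnormal results for the retina and optic nerve results at Baseline and each study visit", again by arm and eye. For the optic disc, "Summary statistics will be provided for the cup-to-disc ratio at each study visit by treatment group and study or non-study eye".
- **BCVA (4.8.5, Table 14.4.2.4):** the actual value and "change from baseline to each on study evaluation will be summarized for the calculated logMAR score", by eye. Under SAP 4.2.1, continuous variables get mean, median, standard deviation, minimum and maximum.
- **IOP (4.8.4, Table 14.4.2.3):** "Counts and percentages of subjects by study eye and non-study eye with elevations in IOP", counted over the whole study, for a rise of at least 10 mmHg and for values above 25 and above 30 mmHg.

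Two other places in the SAP use shift tables. For laboratory data (4.8.2), "Shift from baseline tables to each on study evaluation will be provided by treatment group". The modified BLISS, an exploratory efficacy questionnaire, also has them (Tables 14.2.11.3 and 14.2.11.4).

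SAP 4.6 picks the study eye by the worst sum of eyelid margin vascularity and Total MGD Score. SAP 2.1 says that both eyes are dosed.

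**The concern.** A safety reader wants to know how many subjects who were normal before dosing became abnormal afterwards, and how many lost vision. The slit-lamp and ophthalmoscopy tables answer a different question: what share of eyes of a given label is abnormal on a given day. If some findings resolve while others appear, that share can stay flat.

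This is most plausible for eyelid and conjunctival items. Subjects enter with moderate to severe MGD (Protocol 4.1), and the cream is applied to the eyelid skin. Disease-related lid findings may clear while application-related ones begin.

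The split by eye adds a second gap. The labels come from eyelid scores, treatment is bilateral, and two separate columns do not show whether the same subjects are affected in both.

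With about 42 subjects per arm, a safety signal may consist of a handful of subjects, so subject counts matter.

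**Working it through.** The plan states no event rate or sample-size figure on this point (SAP 4.1 makes no formal calculation), so there is no figure to reproduce. The check is a count of what the planned tables can and cannot determine.

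**Inputs from the documents.** Arm size n = 42 (SAP 2.1). One letter = 0.02 logMAR (Protocol Appendix 4). All event counts below are assumptions for illustration.

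**1. New abnormality from by-visit prevalence.** Let b be the number abnormal at baseline and f the number abnormal at a later visit, with no missing data. The number newly abnormal lies between max(0, f − b) and min(f, n − b).

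| b | f | Newly abnormal | Percent of 42 |
|---|---|---|---|
| 5 | 5 | 0 to 5 | 0% to 11.9% |
| 10 | 10 | 0 to 10 | 0% to 23.8% |
| 10 | 8 | 0 to 8 | 0% to 19.0% |
| 10 | 12 | 2 to 12 | 4.8% to 28.6% |

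One case inside the second row: 4 of the 10 resolve and 4 others become abnormal. Both visits read 10/42 = 23.8%, while 4 of the 42 − 10 = 32 at risk are newly abnormal, which is 4/32 = 12.5%.

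If b = 0, both bounds equal f. The problem disappears, visit by visit, for items that nobody has at baseline.

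**2. Ever affected.** If 2 of 42 (4.8%) are newly abnormal at each of the three post-dose visits, the number ever affected is between 2 (the same subjects) and 2 × 3 = 6 (all different), or 4.8% to 14.3%.

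**3. Either eye.** With 3/42 study eyes and 3/42 non-study eyes affected, the number of subjects is between 3 (full overlap) and 3 + 3 = 6 (no overlap), or 7.1% to 14.3%.

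**4. BCVA.** If k of 42 lose 0.30 logMAR and the rest do not change, the mean change is k × 0.30 / 42.
- k = 2: 0.60/42 = 0.0143 logMAR, and 0.0143/0.02 = 0.71 letter.
- k = 3: 0.90/42 = 0.0214 logMAR, or 1.07 letters.

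In both cases the maximum change in the table is 0.30. The worst loss is therefore visible, but k = 2 and k = 3 are not clearly told apart.

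**5. Table list.** In SAP 7.1, Tables 14.4.2.1, 14.4.2.4 and 14.4.2.5 are the only tables for these three examinations. None is a shift, new-onset, worst-post-dose or vision-loss-category table.

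**The case against.** The case on the other side has several parts.

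- **Adverse events already count subjects.** Ocular treatment-emergent events are tabulated once per subject with no eye split, and the definition covers conditions that worsen after baseline (SAP 4.8.1; Tables 14.3.1.2.2 and 14.3.1.4.2). A reader might infer that either-eye events are counted nowhere; that would be wrong. But neither document says that a new abnormal examination finding, or a given loss of BCVA, must be reported as an adverse event. Events are elicited by open questions (Protocol 8.3) and rest on the investigator's judgement. These tables lessen the gap without closing it.
- **BCVA is not reduced to averages.** A reader might infer that large losses are hidden behind a mean. SAP 4.2.1 also gives the minimum and maximum, so the largest loss is shown. Only the number of subjects is missing.
- **IOP is nearly complete.** It already counts elevations at any time.
- **Offsetting findings are assumed.** No baseline abnormality rate is given, and the exclusions in Protocol 4.2 should make several corneal findings rare at entry. This stands, and it narrows the point mainly to eyelid and conjunctival items.
- **Lid and surface measures do get change from baseline.** Eyelid margin vascularity, corneal staining and bulbar hyperemia are analysed that way, as efficacy. This is true, but none of them replaces the slit-lamp items.
- **Listings cover every assessment, and Protocol 9.5 promises only a summary.** Also true. Listings let a reader trace individual cases, but they give no rate by arm.

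**Conclusion.** The point holds as a gap in tabulation, not in data collection. For slit-lamp and ophthalmoscopy, the planned tables do not determine the number of newly abnormal subjects or the number affected in either eye. With 10/42 at both visits, the first may be anything from 0 to 10. For BCVA, the number of subjects losing vision is missing. For IOP, only the either-eye count is.

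The sizes rest on assumed counts with 42 per arm and no missing data; they show what the tables leave open and do not predict results. A reader might infer from the two eye columns that subject risk is understated by half. That would need equal counts in the two eyes, no subject affected in both, and one column read as subject risk. The documents give no ground for assuming all three, and bilateral dosing makes overlap plausible.

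The trial remains interpretable without the change. It is still worth making, because the examinations concern the treated area and serve the primary objective, and the SAP already applies shift tables to laboratory and BLISS data.

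**What to change.** Before unmasking, amend SAP 4.8.3 to 4.8.6 and the table list in 7.1 to add:

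1. Shift tables by arm and eye: baseline to worst post-dose result for each slit-lamp item, and baseline to Visit 5 or early termination for retina and optic nerve. Ophthalmoscopy is scheduled only at Visits 1 and 5 (Protocol Appendix 1), so its shift is a two-by-two table per item, arm and eye.
2. For each item, the number and percent of subjects newly abnormal in either eye, out of those normal in both eyes at baseline. Subjects with one abnormal eye at baseline remain visible in the shift tables.
3. The number of subjects with BCVA loss from baseline in either eye, at logMAR thresholds that the sponsor chooses and states in advance.
4. An either-eye row in the IOP elevation table (14.4.2.3).

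Keep the by-eye tables as planned. The cost is a few extra table shells and their programming, with no new data. One limit remains: slit-lamp items are coded only as normal or abnormal (Protocol Appendix 5), so these tables will show new abnormalities but not worsening of a finding already abnormal at baseline.
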